6.0 DOSE MODIFICATIONS FOR ADVERSE EVENTS

The Study Chair must be notified of any dosage modification or use of myeloid growth factor.

6.1 Dose Modifications for Hematological Toxicity During Radiation Therapy

For AZD1775 (MK-1775)-related hematologic DLTs, AZD1775 (MK-1775) will be withheld until criteria in 6.1.1 and 6.1.2 are met, and AZD1775 (MK-1775) will be restarted at one dose level lower, if not already at Dose Level -1. If the same DLT is experienced at the lower dose level then AZD1775 (MK-1775) should be discontinued. If a different DLT is encountered, then the patient may restart AZD1775 (MK-1775) at the next lower dose level, if not already at Dose Level -1. Please contact the Study Chair and Operations Center if guidance is required with regard to the day/schedules for AZD1775 (MK-1775) administration in the event the dose is de-escalated.

In the event of hematological DLT, a CBC should be checked at least every other day until recovery of ANC \geq 1,000/mm³ and platelet \geq 100,000/mm³.

A patient who experiences any DLT despite being treated on Dose Level -1 will then complete radiation therapy without AZD1775 (MK-1775). **Radiation is conventional therapy for diffuse intrinsic pontine gliomas and should be continued despite AZD1775 (MK-1775)-related DLT, unless there is a strong clinical contraindication.**

6.1.1 **Radiation should not be interrupted unless clinically indicated.**

6.1.2 **. Radiation should not be interrupted unless clinically indicated.**

6.2 Dose Modifications for Non-Hematological Toxicity During Radiation Therapy

If a patient experiences non-hematological dose-limiting toxicity as defined in [Section 5.5.2](#), AZD1775 (MK-1775) will be withheld until the toxicity resolves to meet eligibility or baseline parameters. Patients may then resume treatment at the next lower dose level. For patients enrolled at Dose Level 1, the dose should be reduced to Dose Level -1. Doses reduced for toxicity will not be re-escalated, even if there is minimal or no toxicity with the reduced dose.

A patient who experiences any DLT despite being treated on Dose Level -1 will then complete radiation therapy without AZD1775 (MK-1775). **Radiation is the standard of care and should be continued despite AZD1775 (MK-1775)-related DLT, unless there is a strong clinical contraindication.**

If toxicity does not resolve to meet eligibility or baseline parameters within 14 days of drug discontinuation, the patient must be removed from protocol therapy.

If the same dose-limiting toxicity recurs in a patient who has resumed treatment at the reduced dose level, the patient must be removed from protocol therapy.

7.0 SUPPORTIVE CARE AND OTHER CONCOMITANT THERAPY

7.1 Concurrent Anticancer Therapy

Concurrent cancer therapy, including chemotherapy, immunotherapy, or biologic therapy may NOT be administered to patients receiving study drug except radiation therapy per study protocol. If these treatments are administered the patient will be removed from protocol therapy.

7.2 Investigational Agents

No other investigational agents may be given while the patient is on study.

7.3 Supportive Care

7.3.1 Appropriate antibiotics, blood products, antiemetics, fluids, electrolytes and general supportive care are to be used as necessary (see [Section 6.0](#)).

7.3.2 Evaluation and management of diarrhea

7.3.3 .

7.3.4 Promethazine, prochlorperazine, and benzodiazepine may still be used as additional adjunctive treatments during AZD1775 therapy.

7.3.5 .

7.3.6 Patients should be strongly encouraged to maintain liberal oral fluid intake.

7.3.7 Suitable alternative medications may be used, with adequate justification, in those studies where the use of any of the above medications might interfere with other study procedures or are deemed insufficient.

7.4 Growth Factors

- . The Study Chair should be notified before growth factors are initiated.

7.5 Concomitant Medications

7.5.1 Anticonvulsants should be used as clinically indicated and tapered as soon as possible. The use of enzyme inducing anticonvulsants is not permitted (See [Appendix II](#)). Prophylactic anticonvulsants are strongly discouraged.

7.5.2 [CYP3A4](#)

7.5.3 [CYP2C19](#)

7.5.4 [Transporters](#)

7.5.5 Herbal Preparations:

Herbal Preparations are not allowed throughout the study. These herbal medications include but are not limited to: St. John's wort, kava, ephedra (ma hung), gingko biloba, dehydroepiandrosterone (DHEA), yohimbe, saw palmetto and ginseng. Patients should stop using these herbal medications 7 days prior to first dose of study treatment.

8.0 EVALUATIONS/MATERIAL AND DATA TO BE ACCESSIONED**8.1 Required Clinical, Laboratory and Disease Evaluation**

All clinical and laboratory studies to determine eligibility must be performed within 7 days prior to enrollment unless otherwise indicated. Laboratory values used to assess eligibility (see [Section 4.0](#)) must be no older than seven (7) days at the start of chemotherapy. The start of chemotherapy is defined as the initiation of treatment with AZD1775 (MK-1775). The start of protocol therapy is defined as the initiation of radiation therapy. Laboratory tests need **not** be repeated if chemotherapy starts **within** seven (7) days of obtaining labs to assess eligibility. If a post-enrollment lab value is outside the limits of eligibility, or laboratory values are older than 7 days, then the following laboratory evaluations must be rechecked within 48 hours prior to initiating chemotherapy: CBC with differential, bilirubin, ALT (SGPT) and serum creatinine. If the recheck is outside the limits of eligibility, the patient may not receive chemotherapy and will be considered off protocol therapy. Imaging studies must be obtained within 14 days prior to start of chemotherapy (repeat the tumor imaging if necessary).

STUDIES TO BE OBTAINED	Pre-Study	During Radiation Therapy
History	X	Weekly
Physical exam with vital signs	X	Weekly
Neurologic exam	X	End of radiation therapy
Height, weight, BSA	X	
Performance status	X	

CBC, differential, platelets	X	Twice weekly (every 3 to 4 days) ²
Urinalysis	X	
Electrolytes including Ca ⁺⁺ , PO ₄ , Mg ⁺⁺	X	Weekly
Creatinine, ALT, bilirubin	X	Weekly
Albumin	X	Weekly
Tumor disease evaluation	X	End of radiation therapy ⁶
Pregnancy test ³	X ³	
Patient diary ⁴		Weekly
Pharmacokinetics ⁵		See Section 8.4
Pharmacodynamics		See Section 8.5
EKG ⁷	X	

¹ See [Table 8.2](#) for required observations during the follow-up period.

² In the event of hematological DLT, a CBC should be checked at least every other day until recovery of ANC \geq 1,000/mm³ and platelet \geq 100,000/mm³ (See [Section 6.1](#)).

³ Women of childbearing potential require a negative pregnancy test negative 3 days prior to enrollment; sexually active patients must use an acceptable method of birth control. Abstinence is an acceptable method of birth control.

⁴ Patient diary (see [Appendix IV](#)) should be reviewed and uploaded into RAVE weekly and after completion of protocol therapy.

⁵ If patients undergo CSF collection anytime while being treated with AZD1775 (MK-1775), patients can opt to send samples for PK evaluation.

⁶ Tumor disease evaluation should be obtained within 3-4 weeks after completion of radiation therapy (within 3-4 weeks after completion of radiation therapy and then according to Table 8.2)

⁷ 12-lead EKG to be obtained at baseline and as clinically indicated

8.2 Required Observations Following Completion of Radiation Therapy

The following studies are required until the patient is off study as defined in [Section 10.2](#).

STUDIES TO BE OBTAINED	30 Days After Last dose of AZD1775 (AZD1775 (MK-1775))	Every 3 Months
History	X	X
Physical exam with vital signs	X	X
Neurologic exam	X	X
CBC, differential, platelets	X	X
Tumor disease evaluation ¹	X ¹	X

¹ Tumor disease evaluation should be obtained within 3-4 weeks after completion of radiation therapy and then every 3 months \pm 14 days.

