2.5 Overview of Proposed Pediatric Study

As outlined above, there are compelling pre-clinical studies that provide the rationale for targeting Wee1 in combination with radiation for the treatment of children with DIPG. Therefore, we propose a phase 1 study of AZD1775 (MK-1775) administered concurrently with focal radiation therapy. We know from prior experience that focal radiation therapy for children with DIPG is generally well tolerated and that radiation therapy by itself has no significant hematological toxicity. In the current phase 1 study we plan to first increase the number of days children are treated with specific Wee1 inhibitor AZD1775 (MK-1775) concurrently with radiation and then dose escalate depending on how well AZD1775 (MK-1775) is tolerated (see the treatment plan in [Section 5.1](#) for details). Due to the unknown pharmacokinetics of AZD1775 (MK-1775) after prolonged administration, the age requirement of the first patient enrolled will be ≥ 7 years. After considering toxicity and results of PK analysis for this patient, we will open the study to children less than 7 years of age.

Radiation therapy is given at the current standard dose of 5400 cGy in 30 fractions of 180 cGy Monday through Friday for a total of 30 fractions over 6 weeks. AZD1775 (MK-1775) will be administered according to the schedule in [Section 5.1](#) after radiation therapy. Dose escalation will occur as outlined in [Section 5.2.1](#). The starting dose of AZD1775 (MK-1775) for this trial was based on 40% of the

adult MTD in the multi-dose schedule of AZD1775 (MK-1775) in combination with chemotherapy in adult patients with solid tumors.

2.6 **Amendment #4B Regarding Escalation of AZD1775 Dosing (2016)**

As of April 2015, 26 patients have been treated on ADVL1217: 6 on Dose Level 1, 6 on dose level 2, 7 on dose level 3 and 7 on dose level 4. To date, the medication has been very well tolerated with minimal side effects. None of the patients treated at dose levels 1-3 experienced dose-limiting toxicity. One patient treated at dose level 4 (AZD1775 95 mg/m² daily Mon-Fri during Weeks 1-6) had a dose-limiting toxicity of grade 3 ALT increase.

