4.0 PATIENT ELIGIBILITY

All clinical and laboratory studies to determine eligibility must be performed within 7 days prior to enrollment unless otherwise indicated. Laboratory values used to assess eligibility must be no older than seven (7) days at the start of chemotherapy. The start of chemotherapy is defined as the initiation of treatment with AZD1775 (MK-1775). The start of protocol therapy is defined as the initiation of radiation therapy. Laboratory tests need **not** be repeated if chemotherapy starts **within** seven (7) days of obtaining labs to assess eligibility. If a post-enrollment lab value is outside the limits of eligibility, or laboratory values are older than 7 days, then the following laboratory evaluations must be re-checked within 48 hours prior to initiating chemotherapy: CBC with differential, bilirubin, ALT (SGPT) and serum creatinine. If the recheck is outside the limits of eligibility, the patient may not receive chemotherapy and will be considered off protocol therapy. Imaging studies must be obtained within 14 days prior to start of chemotherapy (repeat the tumor imaging if necessary).

Important note: The eligibility criteria listed below are interpreted literally and cannot be waived (per COG policy posted 5/11/01). All clinical and laboratory data required for determining eligibility of a patient enrolled on this trial must be available in the patient's medical or research record which will serve as the source document for verification at the time of audit.

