4.1.6 Organ Function Requirements

4.1.6.1 Adequate Bone Marrow Function Defined as:

- Peripheral absolute neutrophil count (ANC) $\geq 1000/\text{mm}^3$
- Platelet count $\geq 100,000/\text{mm}^3$ (transfusion independent, defined as not receiving platelet transfusions for at least 7 days prior to enrollment).

4.1.6.2 Adequate Renal Function Defined as:

- Creatinine clearance or radioisotope GFR $\geq 70\text{mL/min}/1.73\text{m}^2$ or
- A serum creatinine based on age/gender as follows:

Age	Maximum Serum Creatinine (mg/dL)	
	Male	Female
3 to < 6 years	0.8	0.8
6 to < 10 years	1	1
10 to < 13 years	1.2	1.2
13 to < 16 years	1.5	1.4
≥ 16 years	1.7	1.4

The threshold creatinine values in this table were derived from the Schwartz formula for estimating GFR utilizing child length and stature data published by the CDC.²³

4.1.6.3 Adequate Liver Function Defined as:

- Bilirubin (sum of conjugated + unconjugated) $\leq 1.5 \times$ upper limit of normal (ULN) for age.
- SGPT (ALT) $\leq 3 \times$ ULN = 135 U/L. For the purpose of this study, the ULN for SGPT is 45 U/L.
- SGOT (AST) $\leq 3 \times$ ULN = 150 U/L. For the purpose of this study, the ULN for SGOT is 50 U/L.
- Serum albumin ≥ 2 g/dL.

4.1.6.4 Adequate Neurologic Function Defined as:

- Patients with seizure disorder may be enrolled if on non-enzyme inducing anticonvulsants and well controlled. See [Appendix II](#) for a list of recommended non-enzyme inducing anticonvulsants

THIS PROTOCOL IS FOR RESEARCH PURPOSES ONLY, SEE PAGE 1 FOR USAGE POLICY

- Nervous system disorders (CTCAE v5) resulting from prior therapy must be \leq Grade 2 with the exception of tendon reflex (DTR). Any grade of DTR is eligible.

4.1.6.5 Adequate Cardiac Function Defined as:

- $QTc \leq 480$ msec

4.1.6.6 Informed Consent: All patients and/or their parents or legally authorized representatives must sign a written informed consent. Assent, when appropriate, will be obtained according to institutional guidelines.

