5.5 Definition of Dose-Limiting Toxicity (DLT)

DLT will be defined as any of the following events that are possibly, probably or definitely attributable to AZD1775 (MK-1775). The DLT observation period for the purposes of dose-escalation will be the entire duration of radiation therapy.

Dose limiting hematological and non-hematological toxicities are defined differently.

Interruption of Radiation Therapy

Interruption of planned radiation for 5 consecutive fractions or 10 fractions total due to AZD1775 (MK-1775)-attributable toxicity (and not due to technical issues).

Non-Hematological Dose-Limiting Toxicity

5.5.1.1 Any Grade 3 or Grade 4 non-hematological toxicity attributable to AZD1775 (MK-1775) with the specific exclusion of:

- Grade 3 nausea and vomiting of less < 3 days duration (Grade 3 nausea or vomiting \geq 3 days in the presence of antiemetics will be considered a DLT)
- Grade 3 liver enzyme elevation, including ALT/AST/GGT that returns to levels that meet initial eligibility criteria or baseline

THIS PROTOCOL IS FOR RESEARCH PURPOSES ONLY, SEE PAGE 1 FOR USAGE POLICY

within 7 days. See [Appendix X](#) for values that represent thresholds between CTCAE grades.

Note: For the purposes of this study the ULN for ALT is defined as 45 U/L.

- Grade 3 or 4 fever < 5 days duration.
- Grade 3 infection < 5 days duration.
- Grade 3 hypophosphatemia, hypokalemia, hypocalcemia or hypomagnesemia responsive to oral supplementation
- Any Grade 2 non-hematological toxicity attributable to AZD1775 (MK-1775) that persists for \geq 7 days and is considered sufficiently medically significant or sufficiently intolerable by patients that it requires interruption of AZD1775 (MK-1775) for 7 days.
- Note: Allergic reactions that necessitate discontinuation of study drug will not be considered a dose-limiting toxicity.

Hematological dose limiting toxicity

- Grade 3 thrombocytopenia (platelet count < 50,000/mm³)
- Grade 4 neutropenia

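### The DLT rule uses AST and GGT, but neither is scheduled on treatment, and no liver test is scheduled after radiation to detect late events or to settle a final-week Grade 3 rise

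*Combined protocol and SAP*

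**What the plan says.** - **DLT rule (Section 5.5).** Attributable Grade 3 or 4 non-hematological toxicity is dose-limiting. One exclusion is "Grade 3 liver enzyme elevation, including ALT/AST/GGT that returns to levels that meet initial eligibility criteria or baseline", with a limit of 7 days. The window is stated as "The DLT observation period for the purposes of dose-escalation will be the entire duration of radiation therapy".
- **Grading (Appendix X).** ALT, AST and GGT each have grade bands. Grade 3 is 226 to 900 U/L for ALT, 251 to 1000 U/L for AST, and above 5 to 20 times ULN for GGT.
- **Eligibility (Sections 4.0 and 4.1.6.3).** AST has a limit of 150 U/L ("For the purpose of this study, the ULN for SGOT is 50 U/L"), and "All clinical and laboratory studies to determine eligibility must be performed within 7 days prior to enrollment unless otherwise indicated". GGT is not an eligibility test.
- **Schedule during radiation (Section 8.1).** The liver chemistry, pre-study and weekly, sits in the row "Creatinine, ALT, bilirubin". There is no AST or GGT row. The list of tests to be rechecked before the first dose also omits AST.
- **Schedule after radiation (Section 8.2, "Required Observations Following Completion of Radiation Therapy").** The only laboratory row, at 30 days after the last dose and every 3 months, is "CBC, differential, platelets".
- **Follow-up of events (Section 10.1).** Adverse events that are ongoing, or that emerge within 30 days of the last dose, must be followed and reported.
- **Experience so far (Section 2.6).** As of April 2015, one of 7 patients at dose level 4 "had a dose-limiting toxicity of grade 3 ALT increase". No DLT was seen at levels 1 to 3.

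**The concern.** A DLT can be counted only if someone measures it. The rule names three enzymes, and the on-treatment schedule measures one of them plus bilirubin. A site that follows the plan exactly would not look for a Grade 3 rise confined to AST or GGT. Section 11.2 counts a patient without DLT as evaluable once the dose requirement is met and the appropriate monitoring was done. If the Section 8.1 table defines that monitoring, such a patient enters the cohort as free of DLT.

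The cohorts are small. With six patients, the Section 11.3 table escalates on one DLT and de-escalates on two, so a single unseen event can change the decision. The planned dose also rises from 95 mg/m² at level 4 to 200 mg/m² at level 7 (200/95 = 2.1-fold).

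Two further gaps follow the end of radiation. Describing toxicity is primary aim 1.1.2, yet no liver test is scheduled in the 30-day reporting period. And the 7-day recovery test cannot be applied from scheduled data to a Grade 3 rise first seen in the last week.

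**Working it through.** There is no plan figure to reproduce, so the check sets the sections side by side.

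**1. What the rule needs and what is scheduled**

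| Test | In DLT rule (5.5) | Graded (App. X) | Pre-study | During radiation | After radiation (8.2) |
|---|---|---|---|---|---|
| ALT | yes | yes | yes (8.1) | weekly, about 6 | 0 |
| AST | yes | yes | implied by eligibility | 0 | 0 |
| GGT | yes | yes | 0 | 0 | 0 |
| Bilirubin | as general Grade 3/4 toxicity | yes | yes (8.1) | weekly, about 6 | 0 |

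The Appendix X bands agree with the stated ULNs. For ALT, 3, 5 and 20 × 45 = 135, 225 and 900. For AST, 3, 5 and 20 × 50 = 150, 250 and 1000. The mismatch lies in the schedule, not the grading. AST of 251 U/L (Grade 3) with ALT of 225 U/L (top of Grade 2) would be a potential DLT, and scheduled tests would show only the Grade 2 value.

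**2. GGT.** The exclusion needs a return to eligibility level or baseline. GGT has no eligibility level and no scheduled baseline, so from scheduled data neither comparison can be made.

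**3. Final week.** With a Monday start and no missed fractions, week 6 dosing is days 36 to 40. A chemistry drawn then has its 7-day limit at 36 + 7 = day 43 to 40 + 7 = day 47. Both fall after the last fraction, when the weekly schedule has ended. The next scheduled blood draw is 30 days after the last dose, day 40 + 30 = 70. That is 23 to 27 days past the limit, and it has no liver test. For a rise found in weeks 1 to 5, the next weekly draw falls at about day 7, so ALT recovery can be judged if that draw is on time.

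**4. Direction of each gap**
- An isolated AST or GGT rise that is not measured is not counted, so DLTs are undercounted.
- A final-week Grade 3 rise with no documented recovery does not meet the exclusion. Read literally, it is counted as a DLT.
- A rise that first appears after radiation is outside the window and has no effect on the DLT count. It affects the description of toxicity only.

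**5. Illustration of the first gap.** Let p be the true DLT rate and m the share of DLTs missed. The documents do not give m. The observed rate is r = p(1 − m), and P(at most 1 DLT in 6) = (1 − r)^6 + 6r(1 − r)^5. With p = 0.33:

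| m | r | P(at most 1 in 6) |
|---|---|---|
| 0 | 0.330 | 0.358 |
| 5% | 0.314 | 0.391 |
| 10% | 0.297 | 0.427 |
| 20% | 0.264 | 0.501 |

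This describes a full cohort of six, not the whole rolling six design.

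**The case against.** The case for the plan is substantial.

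- **Weekly ALT and bilirubin run through the whole DLT window.** This stands. A reader might infer that the schedule cannot ascertain liver DLTs at all. It can, where they show in ALT or bilirubin.
- **AST is measured at baseline.** This also stands, because eligibility requires it within 7 days before enrollment. What is missing is AST on treatment.
- **The one reported DLT was an ALT rise.** ALT is the enzyme the schedule covers, so that event is not evidence of an AST gap. It shows only that liver enzymes matter in this population.
- **Drug attribution.** Section 9.1.6 lists AST and GGT increases among events with insufficient evidence of a causal link to the drug, and a DLT needs at least possible attribution. Isolated events may be rare. This limits the likely size of the gap but does not remove the mismatch with the protocol's own rule.
- **Follow-up is required anyway.** Section 10.1 covers events that emerge within 30 days as well as known ones, and completion on Day 42 is itself a listed reason for leaving protocol therapy. Section 6.2 (drug held until resolution) and Section 13.4 (resolution dates) presuppose retesting. So a known final-week rise should be followed. But no interval is stated, whereas a hematological DLT has a blood count at least every other day. The continuation of Section 8.1 observations is written for patients removed during radiation, and a silent rise cannot be followed if nothing is scheduled to find it.
- **The number of draws is not fixed.** Missed fractions are made up in week seven or eight, which extends weekly chemistry. Reading one of six draws (17%) as a share of missed events would be wrong, because it counts draws.

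**Conclusion.** The point holds as a documentation and ascertainment gap. AST and GGT are in the DLT rule and in Appendix X but not in the on-treatment schedule. GGT has no reference value for the recovery test. The 30-day visit has no liver test, and no scheduled draw documents 7-day recovery of a Grade 3 rise first found in the final week.

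The size cannot be derived from the documents, which give no frequency for isolated AST or GGT rises. The probabilities above rest on an assumed true rate of 0.33 and assumed missed shares of 0 to 20%.

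A reader might infer that the missing tests after radiation lower the observed DLT rate. They do not: the window ends with radiation, and an undocumented recovery read literally leaves the event as a DLT. A reader might also infer that the liver has the weakest monitoring of any organ system. Urinalysis is pre-study only, and the EKG is done at baseline and as clinically indicated, so that does not hold either. This is a cheap improvement to DLT ascertainment and to primary aim 1.1.2, and it does not call the completed cohorts into question.

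**What to change.** Reconcile Sections 5.5, 8.1, 8.2 and Appendix X:

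1. Add AST to the pre-study and weekly chemistry row in Section 8.1.
2. Settle GGT: either schedule it with a pre-study baseline, or take it out of the DLT rule. The choice is the sponsor's, but the sections must agree.
3. Add ALT, AST and bilirubin to the 30-day visit in Section 8.2, on the draw already taken for the blood count.
4. Schedule a repeat enzyme test within 7 days for any Grade 3 value in the last week of radiation, so that the existing recovery rule can be applied. The 30-day panel comes too late for this.

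The cost is one or two extra analytes on existing samples, a liver panel on an existing draw, and an occasional repeat draw. No dose, DLT threshold or stopping rule needs to change, apart from the listing of GGT if the sponsor takes the second option in item 2.
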